TITLE PAGE

**Role of Linagliptin in improving renal failure by improving
CD34+ stem cell number, function and gene expression in renal
function impaired type 2 diabetes patients**

[name], MRCP (UK), PhD, FACP, FACE

George Washington University Medical Faculty Associates

[name]

[name]

Phone - [contact]

Protocol Version/Date: Version 6.9 / June 2017

PROTOCOL SYNOPSIS

Protocol Title:	Role of Linagliptin in improving renal failure by improving CD34+ stem cell number, function and gene expression in renal function impaired type 2 diabetes patients
Site Numbers & Names:	GWU Medical Faculty Associates
Research Hypothesis:	Both type 2 diabetes and CKD are associated with poor stem cell number and function. Poor viability and function of EPCs in CKD and diabetes affects the repair and regeneration of the endothelium and renal tubules. We hypothesize that use of Linagliptin (along with Insulin, metformin, or both) may help reduce cardiovascular risk by improving EPC survival and function above and beyond adequate glucose metabolism control.
Study Schema: Drugs / Doses / Length of Treatment)	We propose a 2-arm randomized, parallel group, longitudinal study of 12-week intervention duration. The 12-week time interval has been previously shown adequate to observe changes in biochemistry, EPCs and, importantly, pulse wave velocity (PWV) changes. Patients will be randomized to 2 groups: Control, (n=20), Insulin/Metformin + Lifestyle + Placebo. Treatment, (n=20) Insulin/Metformin + Lifestyle + Linagliptin 5mg.

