DPP-4 Inhibitors may have cardio-protective effects of their own, as they increase bio-availability of endogenous GLP-1. They improve blood flow and nitric oxide production in

endothelium (28, 29). These are unique properties not demonstrated by other oral diabetes medications (29). The mechanism underlying these effects may be mediated by increased nitric oxide bioavailability but is not completely known. However these beneficial effects appear to be independent of glycemia reduction.

It is however unknown whether Linagliptin will have any positive effect on human EPC function where two prominent cardiovascular risk factors co-exist such as CKD and type 2 diabetes.

Therefore we plan to investigate if Linagliptin can alter function and gene expression of CD34+ cells in a setting of CKD and type 2 diabetes. We choose to look at non geriatric adult population with early type 2 diabetes (≤ 15 years of duration) at an early phase of renal impairment (stages 1-3).

We specifically choose to exclude known CVD disease patients and early type 2 DM patients with early CKD as this cohort may be still retain capability to reverse or halt persistent endothelial damage seen in type 2 diabetes and CKD (3,30,35).

Our preliminary study results , which just finished, looked at effect of 150min/week of aerobic physical activity on EPCs in pre-diabetes population show that interventions even though non pharmaceutical can lead to quick (within 4 weeks) improvement in gene expression and function of CD34+ cells. These cellular changes are reproducible and consistent with other outcome measures such as serum biochemistry and vessel wall dilation measures such as flow mediated dilatation. (34)

Research Hypothesis:

We hypothesize that Linagliptin, a member of DPP-4 inhibitor group of drugs may be able to improve number and function of CD34+ endothelial progenitor cells by up-regulating chemotactic agent SDF1 alpha (DPP-4 degrades SDF-1) and its receptor CXCR4 (7, 20, 21) and thereby improving EPC migration and overall endothelial function. We also propose that this expected cardiovascular benefit is independent of HbA1C reduction. (30, 31)

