Recruitment: Subjects will be recruited from the physician clinics at GWU, Medical Faculty Associates, where [name] is a clinician, as well as through referral from the VA. All patients will receive counseling regarding the study aims and methods.

Study Design Overview: We propose a 2-arm randomized, double-masked, placebo-controlled, parallel group, longitudinal study of 12-weeks duration. (See study design below), recruited over 3 years. The 12 week time interval has been previously shown adequate to observe changes in endothelial progenitor stem cells, biochemistry and importantly, PWV changes [20, 36]. Patients will be randomized to 2 groups:

Control, (n=20), Insulin/Metformin/Both + Lifestyle + Placebo

Treatment, (n=20) Insulin/Metformin/Both + Lifestyle + Linagliptin 5mg

This proposed study is based on patients with type 2 diabetes of ≤ 15 years duration, who are on stable dose of insulin, Metformin, or both for at least 3 months but still remain poorly controlled with HbA1C between 6.5% and 10% (both inclusive), but not overtly out of control ($> 10\%$ of HbA1C). Our study design is similar to that of Fadini et al [20] where Sitagliptin was compared to placebo with endothelial progenitor cells as an outcome measure in patients with type 2 diabetes over 4 weeks.

Though our study is over 12 weeks we do not anticipate significant drop in HbA1C in between the two groups in this relatively short time period to act as a confounding factor on CD34+ cell number, function and gene expression.

Most clinical studies looking at HbA1C reduction were of a much longer duration of 6 months or above and most DPP-4 inhibitor studies are with animal EPCs where comparison with human CD34+ population is difficult to make. In one study (58) where saxagliptin was used for **12 weeks** in drug-naïve type 2 diabetes patients there was placebo-subtracted HbA1c reduction noted of 0.45-0.63%. It showed mean placebo-subtracted reductions in fasting serum glucose of 20 mg/dL. From our laboratory studies of in vitro human EPC studies we do not think glucose level change of 20 mg/dL is significant enough to account for changes in EPC number, function and gene expression. However we will take the possibility of glycemia change/ reduction in experimental arm into account during statistical analysis of the results between the Linagliptin and placebo groups.

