In the event that TIME is modeled using indicator variables, two indicator variables will be used to represent the three time points, with baseline serving as the reference category. The interaction between GROUP and TIME will be modeled in a similar fashion using two additional indicator variables. The above multivariable model enables us to adjust for time-varying covariates, such as glucose. Since glucose will be measured contemporaneously with the outcomes at each visit, however, causal interpretations of glucose and any outcome are suspect. As such, we will consider glucose as a nuisance covariate, and consider any relationship between glucose and an outcome as merely associative.

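### Independence of benefit from HbA1c cannot be concluded from the analysis as written: the arms may separate in glycaemia by week 12, and adjusting for concurrent glucose does not settle the question

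*Combined protocol and SAP*

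**What the plan says.** Two hypothesis statements separate the cellular benefit from glucose lowering. The Protocol Synopsis (Research Hypothesis) speaks of "improving EPC survival and function above and beyond adequate glucose metabolism control". The Introduction (Research Hypothesis) adds: "We also propose that this expected cardiovascular benefit is independent of HbA1C reduction".

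Section 4.5 (Study Design Overview) then deals with glycaemia in four moves:

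- It states the expectation for the treatment period: "we do not anticipate significant drop in HbA1C in between the two groups in this relatively short time period to act as a confounding factor".
- It cites a 12-week saxagliptin study in drug-naive patients, in which "there was placebo-subtracted HbA1c reduction noted of 0.45-0.63" per cent. On glucose: "It showed mean placebo-subtracted reductions in fasting serum glucose of 20 mg/dL".
- It judges this too small to matter, from the investigators' own in vitro studies: "we do not think glucose level change of 20 mg/dL is significant enough to account for changes in EPC number". No data are shown.
- It promises to deal with the matter anyway: "However we will take the possibility of glycemia change/ reduction in experimental arm into account during statistical analysis".

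The method appears in section 5 (Data Analysis). Glucose may enter the mixed model as a time-varying covariate. Because it is measured at the same visits as the outcomes, the plan says that "causal interpretations of glucose and any outcome are suspect". It treats glucose as a nuisance covariate and any link with an outcome as association only. HbA1c is a planned measurement (Synopsis and section 2.2) but is not named as a covariate.

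**The concern.** Independence from HbA1c reduction is a causal statement: some or all of the effect on the cells reaches them by a route other than lower glucose. To support it, a trial must either keep glycaemia equal between arms or have an analysis that can separate the two routes. The plan's expectation for 12 weeks sits badly with the only 12-week figure it cites, and the one analysis it offers is, by its own account, not open to causal reading.

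What is at stake is the interpretation and not the main estimate. A positive CD34+ result could be described as glucose-independent when the data cannot distinguish that from an effect passing partly through glucose.

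**Working it through.** **1. The passages side by side.** The expectation in section 4.5 can be read as no HbA1c difference, or as no difference large enough to drive the cells. On the first reading, the cited 0.45-0.63% speaks against it. On the second, everything hangs on the in vitro judgement about 20 mg/dL, for which no data are given. The remark that most HbA1c studies ran for six months or more does not show that 12 weeks is too short. The 0.45-0.63% is a literature value and cannot be recomputed. It carries reference number 58, which in the list is a paper on methods of measuring resting energy expenditure, so its source cannot be traced.

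**2. Does anything hold glycaemia equal?** Entry HbA1c spans 6.5-10% (section 3.2.1). Insulin titration is tied to the 10% level (Introduction; sections 3.1 and 4.5). Of the 40 patients, 22 are planned to be on metformin alone (section 5, sub-group breakdown). No glycaemia-matched arm, HbA1c equivalence margin or mediation analysis is planned.

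**3. What could an HbA1c comparison show with 20 per arm?** The plan gives no SD for HbA1c, so I assume an SD of change of 0.8-1.2%. As a plausibility check, a uniform spread over 6.5-10% has SD 3.5/√12 = 1.01. With the correlation of 0.60 that the plan assumes for its outcome measures, the SD of change is 1.01 × √(2 × 0.4) = 0.90.

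The half-width of the 95% confidence interval is 2.024 × SD × √(2/20), where 2.024 is the t quantile on 38 degrees of freedom. Power is for a two-sided 5% two-sample t-test.

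| Assumed SD | CI half-width | Power, true 0.45 | Power, true 0.63 |
|---|---|---|---|
| 0.8 | 0.51 | 41% | 68% |
| 1.0 | 0.64 | 28% | 49% |
| 1.2 | 0.77 | 21% | 37% |

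Even an observed difference of exactly zero would not exclude 0.45 at any of these SDs, nor 0.63 at SD 1.0 or 1.2. A real separation of the cited size would be non-significant in 32% (1 − 0.68) to 79% (1 − 0.21) of such trials. These figures are illustrative. The planned model uses three visits, but with complete data at weeks 0, 6 and 12 a patient's fitted linear slope is the week 0-to-12 change divided by 12, so the comparison is close to the planned one.

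**4. What could adjustment for glucose show?** Start from the plan's own effect: 5/wk against 4/wk over 12 weeks gives (5 − 4) × 12 = 12 cells, as section 5 states.

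- *Imperfect marker.* Suppose all 12 cells run through glycaemia and the model adjusts for a marker of it with reliability r. The remaining arm effect is 12 × (1 − r): 1.2, 2.4 and 3.6 cells at r = 0.9, 0.8 and 0.7. This would look like an independent effect although none exists.
- *Common cause.* Suppose the drug does nothing to the cells, but an unmeasured factor loads c on both glycaemia and cells. With a separation of 0.54 (midpoint of 0.45 and 0.63), a glycaemia SD of 0.9 and the plan's cell SD of 15, the adjusted arm effect is 15 × c² × 0.54/0.9 = 9c²: about 0.8, 2.3 and 4.4 cells at c = 0.3, 0.5 and 0.7. The sign reverses if the factor moves glycaemia and cells in opposite directions.

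Reliabilities and loadings are assumptions. Both cases show that adjusting for a variable measured after randomisation can leave or create an apparent direct effect.

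**The case against.** The case for the plan is a fair one, and several stronger readings that a reader might draw are not supported.

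- *That the independence hypothesis rests only on the short duration.* It does not. The Introduction also gives a mechanism (SDF-1 alpha and CXCR4) and cites literature, and section 4.5 adds the in vitro argument and the promise of adjustment. These are reasons to propose the hypothesis; they do not give the trial a way to establish it.
- *That the plan forecasts a 0.45-0.63% separation between its own arms.* It does not. The figure is from another drug in drug-naive patients, whereas these patients take insulin, metformin or both, with a four-week lead-in and insulin titration allowed. It is a warning figure.
- *That the main comparison is confounded.* The plan itself uses that word, but an HbA1c change caused by the drug lies on the path from treatment to outcome. The randomised comparison of CD34+ cells is unharmed, and the primary objective, the effect of adding linagliptin, does not need independence.
- *That a non-significant HbA1c difference will be read as independence.* The plan nowhere says so. The table guards against a possible misuse and does not describe a planned analysis.
- *That no analysis could inform the question.* A pre-specified mediation analysis with stated assumptions could, though imprecisely with 40 patients.

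It also counts for the plan that it calls itself a pilot and already cautions against causal reading of glucose. That caution is sound, but it leaves the two hypothesis statements without an analysis to support them.

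**Conclusion.** The concern holds for the independence claim only. The expectation stated for 12 weeks conflicts with the sole 12-week figure cited beside it. That figure is set aside without data, and adjustment for concurrent glucose cannot show that benefit is independent of HbA1c. The total effect of linagliptin on CD34+ cells remains validly estimated.

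On size: under an assumed SD of HbA1c change of 0.8-1.2% and 20 complete patients per arm, the between-arm HbA1c difference would be known only to about ±0.5 to ±0.8 points, which is as wide as or wider than most of the cited separation. If the whole 12-cell effect ran through glycaemia, a marker of reliability 0.7-0.9 would still leave 1.2-3.6 cells apparently unexplained. The conclusion itself does not depend on these assumed values: it follows from the absence of any planned analysis that could support a causal reading. The change should be made, because it alters what the trial may claim.

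**What to change.** 1. In section 4.5, revise the sentence on HbA1c to say that a between-arm separation of the order cited is possible, note that the figure comes from another drug in drug-naive patients, and correct its reference. Do not enter 0.45-0.63% as the expected difference.
2. In the Synopsis and Introduction, state the hypothesis to be tested as the total effect of adding linagliptin on CD34+ cells. Label independence from glycaemia exploratory.
3. Report between-arm differences in HbA1c and fasting glucose at weeks 6 and 12, with 95% confidence intervals, beside the cellular results. State that a non-significant HbA1c difference is not evidence of independence.
4. Pre-specify any glucose-adjusted, HbA1c-adjusted or mediation analysis as exploratory, with its assumptions written out, and keep it apart from the unadjusted-for-glycaemia treatment effect.

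The cost is protocol wording and a few table rows. Section 4.5 already has all primary and secondary measures, which include HbA1c and fasting glucose, taken at weeks 0, 6 and 12, so no patients or visits are added. The sponsor gives up a stronger claim, but one that the analysis as written could not have supported.

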2. CD34
3. CD309 (VEGFR2-KDR)
4. CD184 (CXCR4), receptor substrate for SDF1 alpha
5. CD31 (PECAM-1, a mature circulating endothelial cell marker)
6. CD133 (a progenitor marker)
7. CD144 (Vascular Endothelial cadherin)
8. Sytox Blue OR Propidium Iodide staining (to detect apoptotic cells)
9. Combinations of 2+3+4+8, to assay percentage of double or triple positive cells
10. (3+4+5+8), to assay percentage of double or triple positive cells
11. 500,000 CD34+ cells, post column will be stained with – PE labelled + Sytox Blue (as a quality control measure, post column)

B. Plate 5 million cells in each well of a 6 well or 12 well plates (2 million) BD Biosciences Human Fibronectin coated plate, total 2 wells, total 10 million mononuclear cells (prior to CD34 magnetic bead sorting) using CFU Hill Colony forming unit (Stem Cell Technologies- Cat#05900) media for Colony Forming unit (CFU) Assay. 2 days post plating, harvest non-adherent cells from each well, counted and will be replated at 1.0×10^6 cells/well in 12-well fibronectin coated plate. It is important that cell number of 1.0×10^6 is maintained in each well. CFU needs to be counted on Day 7 post plating (from initial plating).

From CD 34+ cell population (Post Sorting):

A. Migration Assay using SDF1 Alpha concentrations of 0, 10, 100ng/ml using 100,000 cells in 300ul serum free cell suspension media per insert. If sufficient cells are available we will note migration in response to VEGF-A (0, 20, 50 ng/mL).

SDF1 Assay alone will need $100,000 \times 9 = 0.9$ million cells. Use triplicates.

We will use 24 well plate using 3 micron pore migration membrane inserts from BD or Corning (354575).

Genes to be assessed on CD34 positive, CD34 negative cells:

Endothelial lineage cell surface markers: CD34, VEGFR2 (KDR), CD31, CD144

For Anti-oxidant gene expression: Superoxide dismutase (SOD) 1, 2 and 3, catalase, glutathione- peroxidase.

Apoptosis pathway: p53, p21, Bcl2, caspase-3

Endothelial Function Assay Gene: eNOS

Genes associated with progenitor cell chemotaxis: VEGF-A, SDF1 alpha, CXCR4

Secondary Measures:

- Highly selective C-reactive protein (hs-CRP), IL-6, IL-10, TNF-alpha, and fasting lipid profile including ApoA1 and ApoB (3, 6)
- Serum SOD activity and SDF1 alpha (ELISA), VEGF-A (ELISA) and GLP-1 (ELISA) levels will also be assessed (14, 20, 24, 39).
- Assessment of insulin sensitivity using the HOMA-IR (32), calculated from individual serum measures (fasting glucose (mg/dl)* insulin (μU/mL)/405) [37].
- Adiposity will be measured using the Tanita Body Composition Analyzer scale, measured as percentage body fat, BMI, waist-hip measurements (5, 55)
- Fasting lipid profile will be checked as a marker of insulin resistance and lipotoxicity at weeks 0, 6 and 12.
- We also intend to acquire Pulse wave analysis and Vascular Flow using SphygmoCor CP system from ATCOR to measure central arterial pressure and arterial stiffness (38-42). The secondary measures are indirect measures of endothelial inflammation in early type 2 diabetes patients. (30, 31, 55, 56, 57).
- Obtain indirect calorimetric measurements of basal metabolic rate using machine obtained from Korrs Medical. This is a non invasive procedure. We plan to measure the oxygen that the body consumes. It will help us calculate a patient's Resting Energy Expenditure (REE), commonly referred to as a Resting Metabolic Rate (RMR). As our protocol is directed to overweight and obese individuals using incretin therapy, it will be beneficial to note if the treatment modifies RMR. Description: The machine ReeVue by KORR directly measures the concentration of oxygen breathed out by each patient. The patient breathes through a simple mouthpiece as all the exhaled air is collected and analyzed. Because there is a direct correlation between oxygen consumed and calories burned (4.813 calories for every milliliter of oxygen consumed), an accurate measurement of oxygen consumption is an effective measurement of calorie consumption. The machine uses a one-way valve in the disposable (MetaBreather) mouthpiece. This draws in fresh room air with each inspiratory breath and eliminates concerns about cross contamination. The disposable mouthpiece is thrown away. It is unnecessary to clean the equipment or the tubing between each patient. This

equipment is FDA approved and has been used in physician offices as an oxygen uptake test with associated CPT code #94690. (58)

- Urine pregnancy testing for women of child bearing potential
- Creatinine Clearance and proteinuria estimation via random spot urine.

We will obtain a total of 85 mL of peripheral blood per visit. Of these 85 mL, 60 mL will be used to obtain CD34+ cells from MNC population and 25 mL for biochemistry and serum ELISA assays.

We may obtain 95mL of peripheral blood at visits 2 and 3 if necessary, and the patient agrees. Of this 95mL, 75mL will be used to obtain CD34+ cells from MNC population and 20mL for biochemistry and serum ELISA assays.

4.7 Study Materials

BI, manufacturers of Linagliptin are expected to provide Linagliptin and matching placebo at no cost for this study.

4.8 Safety Assessments

Study drug toxicities will be assessed continuously. Adverse events will be evaluated on a continuous basis while the patient is on study and until 30 days after the last dose of study drug. Patients should be followed until all treatment-related adverse events have recovered to baseline or are deemed irreversible by the principal investigator.

5 STATISTICAL CONSIDERATIONS

Statistical Analysis:

Sample Size Estimation:

The total sample size requested, accounting for attrition over the 12-week period, is 20 subjects per group or 40 subjects total. We plan to allow for 25% attrition (drop out), therefore plan to screen 55 patients over three years.

Sample size estimates were based on the effects of exercise on CD34+/KDR+ cells and VEGF, as described in the literature (47-50).

This is a pilot study and accurate power calculation is not feasible.

The effect of a single session, as well as extended training, on healthy subjects or those with existing cardiovascular conditions appears to increase the CD34+/KDR+ cells and VEGF.

To compute sample size we used the approach suggested by Diggle, Liang, & Zeger (1994)(51) which compares the rates of change in the two study groups over time. This approach incorporates the number and interval of time points and the correlation among repeated measures. For this study, we will employ one baseline and two follow-up measures at 6 and 12 weeks. Further, we will assume a correlation 0.60 among repeated measures of the outcome. We consider this a conservative estimate since Frison and Pocock (1992) (52) suggest a correlation of 0.65 as reasonable in the absence of an existing estimate. We also note that as this correlation increases, statistical power also increases.

The results in the table below show the expected mean difference in study groups at the end of follow-up, as well as the average rate of change in the two groups at 80% power and 90% power. To estimate the effect of Linagliptin on the CD34+/KDR+ cells, we expect that the effect would be at least 25% greater than the effect seen for exercise alone. Using the results from Sandri et al. (2005)⁴⁹ for the rate of change and the variability, the CD34+/KDR+ cells increased an average rate of about 4/wk with a standard deviation of about 15. Thus, for a 25% increase in the rate of change for the CD34+/KDR+ cells due to Linagliptin, a sample size of 18 subjects per group would provide about 84% power, assuming measures taken at baseline and 2 equally-spaced time points over 12 weeks. At the conclusion of follow-up, we would expect study groups to differ by an average of 12 cells. If the effect of Linagliptin is only 20%, a sample of 18 would provide about 70% power, whereas a sample of 20 would provide about 73% power.

For VEGF, the results from Sandri et al. (2005)(49) were mixed with one study group showing a .6 pg/mL per week increase and another showing a 0.5 pg/mL per week decrease after 4 weeks of training. If we assume that Linagliptin will increase VEGF consistently at 0.3 pg/mL per week difference in slopes compared with exercise alone, then assuming a standard deviation of 5 and correlation or 0.60 among repeated measures, a sample size of 18 per group would provide about 77% power to detect a difference in slopes of 0.3 pg/mL per week or a mean difference in the groups at the end of the study of 3.6 pg/mL. A sample size of 27 would provide about 90% power to detect the same effects.

Thus, we feel that a sample size of at least 18 subjects per group with complete data would provide sufficient power for the study outcomes. In order to insure that we will have 18 per group who complete the study, we will enroll 20 subjects per group in order to account for attrition over the 12-week intervention period.

Biochemical Measure	Mean difference at end of 12 weeks	Sample Size per group	Power
CD34+/KDR+	12 cells	18	0.84

cells	(25% increase; 4/wk vs. 5/wk)	22	0.90
VEGF, pg/mL	3.6 pg/mL (50% increase; (0.6/wk vs. 0.9/wk)	18	0.77
		27	0.90

Sub-Group Subject Number Breakdown:

To estimate the effect of linagliptin on CD34+/KDR+ cells, we originally proposed a sample size of 20 per group in 2 groups, giving us power = .73, assuming alpha=.05, between time points of .60 and equal allocation between groups. Thus, the group x time interaction effect size we were modeling was an interaction that explained 3% of total variance, or a partial eta-square = .0291. Using 3 groups (Insulin only, metformin only, metformin + insulin), with the same effect size, we would achieve this same level of power using a total sample size of 51 (17 per group). However, given the relatively small numbers of potential participants with insulin-only (n=21) and insulin+metformin (n=54), and the relative large number with Metformin only (260), we will need to change the allocation ratio between groups. Maintaining the same total sample size as originally proposed (40), we will allocate patients from each group in the following numbers: **Metformin only (22), Metformin+insulin (12), Insulin only (6)**. We recognize that we will be underpowered for comparisons between the Metformin + insulin versus Insulin groups. However, comparisons with the Metformin-only group will still have reasonable power. Given the small number of potential patients with Insulin-only, this is a feasible strategy for including this group in the analysis.

Data Analysis.

The distributional assumptions of all measures will be examined. Means and standard deviations will be computed for continuous measures and proportions for categorical variables. Graphical representations of the mean group slopes and individual slopes will be generated and inspected. Study groups will be compared to determine whether any imbalance between the groups on patient characteristics remain after randomization. If imbalance is evident, by inspection, all models will be adjusted for the unbalanced covariates. Change in outcome over time will be examined using a multilevel approach with linear mixed models (LMM) (53, 54). The longitudinal multilevel modeling approach will enable us to examine characteristics of within-person change, as well as between-group differences that may influence change. LMMs handle missing data more efficiently than traditional ANOVA designs. In the linear mixed models, the patient is considered a random effect and the outcome measured at specific time points is nested within patient. In an initial model containing only the variable TIME, we will use a likelihood ratio test to determine whether a random effect for time should be modeled.

The model below represents a random intercept for patient and a random coefficient for TIME.

$$Y_{ij} = \beta_0 + \beta_1 Time_{ij} + u_{i0} + u_{i1} Time_{ij} + \varepsilon_{ij}$$

We will examine whether TIME may be modeled linearly by testing the added contribution of TIME (represented with two indicator variables) to a model with TIME as a single continuous variable. Assuming time may be modeled as a continuous variable, subsequent analyses will add study group and other patient characteristics as covariates. We are particularly interested in whether there is a significant interaction between study group and time, adjusting for other patient level covariates. A significant interaction would indicate that the slopes in outcome over time differ by study group. If the global test of interaction is significant, subsequent significance testing of the pairwise comparisons of group slopes group will be adjusted for multiple comparisons. The model also includes coefficients for the group-by-time interactions and random effects for patient and time.

$$Y_{ij} = \beta_0 + \beta_1 Time_{ij} + \beta_2 Group_i + \beta_3 (Time_{ij} \times Group_i) + u_{i0} + u_{i1} Time_{ij} + \varepsilon_{ij}$$

In the event that TIME is modeled using indicator variables, two indicator variables will be used to represent the three time points, with baseline serving as the reference category. The interaction between GROUP and TIME will be modeled in a similar fashion using two additional indicator variables. The above multivariable model enables us to adjust for time-varying covariates, such as glucose. Since glucose will be measured contemporaneously with the outcomes at each visit, however, causal interpretations of glucose and any outcome are suspect. As such, we will consider glucose as a nuisance covariate, and consider any relationship between glucose and an outcome as merely associative.

